10.3.1.3 Summary of Treatment-Emergent Adverse Events by Severity

All subjects reporting TEAEs will be summarised by severity of TEAE (mild, moderate or severe) and study part. Counts will be given for number of subjects, not number of events. Counts will be given by maximum severity (ie subjects experiencing more than 1 TEAE within a study part will be counted only once using the most severe episode).

Additionally, subjects reporting TEAEs will be summarised for SOC and PT by maximum severity (ie mild, moderate or severe) and study part. Counts will be given for total number of subjects, not for events. Counts by maximum severity will be given (ie subjects experiencing more than 1 TEAE within a study part will be counted only once within each SOC and PT using the most severe episode).

10.3.1.4 Summary of Treatment-Emergent Adverse Events by Relationship to IMP

All subjects reporting TEAEs will be summarised by relationship to IMP (ie unrelated, possibly related and related) and study part. Counts will be given for number of subjects, not number of events. Counts will be given by the closest relationship to IMP (ie subjects experiencing more than 1 TEAE within a study part will be counted only once using the most closely related event).

Additionally, subjects reporting TEAEs will be summarised for SOC and PT by closest relationship to IMP (ie unrelated, possibly related or related) and study part. Counts will be given for total number of subjects, not for events. Counts by closest relationship will be given (ie subjects experiencing more than 1 TEAE within a study part will be counted only once within each SOC and PT using the most closely related event).

10.3.1.5 Summary of Adverse Drug Reactions

All subjects reporting ADRs will be summarised by study part. Counts will be given for number of subjects and number of events. Subjects experiencing more than 1 ADR within a study part will be counted only once for number of subjects but will be counted more than once for number of events.

Additionally, subjects reporting ADRs will be summarised for SOC and PT by study part. Counts will be given for number of subjects and number of events. For programming purposes counts of number of subjects will be by maximum severity (ie subjects experiencing more than 1 episode of a TEAE within a study part will be counted only once within each SOC and PT using the most severe episode).

10.3.1.6 Summary of Serious Adverse Events

All subjects reporting serious adverse events (SAEs) will be summarised by study part. Counts will be given for number of subjects and number of events. Subjects experiencing more than 1 SAE within a study part will be counted only once for number of subjects but will be counted more than once for number of events.

Additionally, subjects reporting SAEs will be summarised for SOC and PT by study part. Counts will be given for number of subjects and number of events. For programming purposes counts of number of subjects will be by maximum severity (ie subjects experiencing more than 1 episode of a SAE within a study part will be counted only once within each SOC and PT using the most severe episode).

10.3.2 Listings for Adverse Events

All pre-dose AEs (as defined in Section 10.3) will be listed including SOC and PT.

A separate data listing of all TEAEs will be provided for each study part including the SOC and PT. In addition a listing of all SAEs will be provided.

10.4 Laboratory Evaluations

The details of sample collection for laboratory safety analysis are described in the study protocol.

Where a value is provided by the safety laboratory as either above or below the limit of detection this will be set to the limit of detection itself for summary purposes. No imputations will be made in the individual listings.

10.4.1 Summary Tables for Laboratory Evaluations

Haematology and clinical chemistry data will be summarised (n, mean, SD, median, minimum and maximum) for each laboratory parameter at each time point, including changes from baseline (Day 1, Pre-dose for each study part) to Day 3 in Part 1 and Day 8 in Part 2 by study part. Shift tables from baseline to Day 3 in Part 1 and Day 8 in Part 2 by study part (with respect to the number and percentage of subjects with values below, within or above the reference range) will be presented by study part. Percentages will be based on the number of subjects with measurements at baseline and the relevant post-baseline time point.

Reference ranges for each laboratory parameter will be presented for the relevant parameter in each summary table.

10.4.2 Listings for Laboratory Evaluations

The sample collection data (eg collection times) for laboratory analysis and urinalysis data will be listed.

All individual subject data, for planned haematology, clinical chemistry, and urinalysis data including derivations such as change from baseline will be listed. If applicable, data from unscheduled laboratory tests will also be listed and flagged with a "#" to indicate it will not be used in the summary statistics. In these listings, individual data will be flagged with an "H" or an "L" for values that are higher or lower than their reference ranges, respectively.

Separate listings of all haematology, clinical chemistry and urinalysis values outside their reference ranges by subject will also be provided. References ranges will be supplied by the safety laboratory for haematology and clinical chemistry and per the database for urinalysis (ie a positive or negative result) with the exception of the following reference ranges for urinalysis:

- pH: 5.0 to 9.0
- Specific gravity: 1.000 to 1.030

10.5 Vital Signs

The details of measurement of supine vital signs are described in the study protocol.

10.5.1 Summary Tables for Vital Signs

Vital signs data (ie systolic and diastolic blood pressure [BP], heart rate and oral body temperature), including change from baseline (Day 1, Pre-dose for each study part), will be summarised (ie n, mean, SD, median, minimum and maximum) at each post-baseline time point by study part.

In addition, the number of subjects with 'substantial' increases or decreases or no substantial change from baseline in systolic BP ($>\pm 20$ mmHg), diastolic BP ($>\pm 10$ mmHg) and heart rate ($>\pm 15$ bpm) will be summarised.

10.5.2 Listings for Vital Signs

All individual vital signs data (ie systolic and diastolic BP, heart rate and oral body temperature), including derivations such as change from baseline will be listed. Individual data will be flagged with an "H" or an "L" for values that are higher or lower than their reference ranges, respectively, and subjects with 'substantial' increases or decreases from baseline (as defined in Section 10.5.1) in systolic BP, diastolic BP and heart rate will be flagged with an "I" (increase) or "D" (decrease), respectively. If applicable, data from unscheduled vital signs assessments will also be listed and flagged with a "#" to indicate it will not be used in the summary statistics.

In addition, a separate listing of all vital signs data outside their reference ranges by subject will also be provided.

The reference ranges (from the Quotient SOP "The Interpretation of the Electrocardiogram, Vital Signs and Clinical Laboratory Data During Phase I / II Clinical Trials") defined in Table 4 will be used.

Table 4 Vital Signs Reference Ranges

Parameter	Split	Lower limit	Upper limit
Systolic BP	18-45 years	90 mmHg	140 mmHg
Systolic BP	>45 years	90 mmHg	160 mmHg
Diastolic BP	NA	40 mmHg	90 mmHg
Heart rate	NA	40 bpm	100 bpm
Oral Body Temperature	NA	35.5°C	37.5°C

NA=Not applicable

10.6 ECGs

The details of measurement of supine ECG parameters (ie ventricular rate, QT interval, QTcF interval, PR interval, QRS duration, QRS axis and interpretation) are described in the study protocol. ECG parameters will be reported in the order given above in both summary tables and data listings.

10.6.1 Summary Tables for ECGs

ECG data, including change from baseline (Day 1, Pre-dose for each study part), will be summarised (ie n, mean, SD, median, minimum and maximum) at each post-baseline time point by study part. The number and percentage of subjects with normal and prolonged QT intervals corrected for heart rate using Fridericia's correction (ie QTcF) and increases in QTcF intervals from baseline within the categories defined in Table 5 (based on the International Council on Harmonisation [ICH] E14 guideline [1]) will be summarised by time point within each study part. Percentages will be based on the number of subjects with measurements at the relevant time point.

For 'Overall' counts the worst (highest) value for each subject will be used for the counts. For the parameter 'Increase in QTcF interval from baseline', decreases in QTcF value fall into the <30 category (ie every subject should appear once in this summary table and actual change rather than absolute change is used for this parameter).

Table 5 ICH E14 Ranges for QTcF Intervals

Parameter	ICH E14 Range
QTcF intervals	≤450 msec
	451-480 msec
	481-500 msec
	>500 msec
Increase in QTcF interval from baseline	<30 msec
	30-60 msec
	>60 msec

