8.3 Subject Withdrawal

If a subject wishes to leave the study at any time, they will be permitted to do so. Every reasonable effort will be made by Quotient Sciences to complete a final assessment/discharge procedures. Quotient Sciences will advise the sponsor of the withdrawal of any subject from the study.

Early withdrawal is defined as the date of the decision to withdraw the subject from the study. Subject completion is defined as the date of the last procedure conducted or last contact (ie phone call/visit) for that subject.

If a subject requests to leave the clinical unit earlier than the planned discharge time eg due to unforeseen personal circumstances, but aims to return to the unit to complete the study, this will be documented as a subject self-discharge and a protocol deviation. The subject must complete the planned assessments/discharge procedures before discharge from the clinical unit and will return for the next study period/assessments, as planned.

Subjects will be withdrawn from the study drug(s) for the following reasons:

- Experiencing a serious or severe AE including but not limited to:
 - corrected QT (QTc) interval of >500 msec or increase in QTc interval of >60 msec from baseline (confirmed following a repeat ECG)
 - ALT concentration >3 x the upper limit of the reference range
- Termination of the study
- Upon the subject's request (withdrawal of consent)
- Significant deviation from the protocol
- Concurrent illness or requirement for prohibited medication
- At the discretion of the investigator/sponsor

For the purpose of withdrawal criteria in Parts 1 and 2, baseline will be considered as the pre-dose Day 1 measurement for each part.

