14.7 ECG Measurements

12-lead ECGs will be measured after the subject has been in the supine position for a minimum of 5 min according to the time schedule presented in Appendix 2 and Appendix 3.

The acceptable deviations from the nominal ECG measurement time points are:

- The pre-dose ECG measurements will be taken ≤ 2 h before dosing
- Post-dose ECG measurements will be taken ± 15 min from the nominal post-dose time point
- Discharge ECG measurements will be taken ± 1 h from the nominal time point.

If a subject shows an abnormal assessment at any stage, repeat measurements may be made and the abnormality followed to resolution if required. Additional measurements may be taken as deemed necessary by the investigator.

Any clinically significant abnormality, including changes from baseline, will be reported as an AE.

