14.10 Additional Safety Procedures

Additional non-invasive procedures that are already specified in the protocol may be performed, if it is believed that an important effect of the IMP(s) is occurring or may occur at a time when no measurements are scheduled, or if extra procedures are needed in the interests of safety.

Additional blood samples for safety assessments may be taken if required by the investigator at any point.

15 Statistics and Data Analysis

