10.6.2 Listings for ECGs

All ECG measurements (ie single readings), including derivations such as change from baseline, will be listed.

All ECG measurements will be flagged with an "H" or an "L" for values that are higher or lower than their reference ranges, respectively. If applicable, data from unscheduled ECG assessments will also be listed and flagged with a "#" to indicate it will not be used in the summary statistics.

In addition, subjects with increase in QTcF interval from baseline (30-60 msec) and with 'substantial increases' (>60 msec) will be flagged with 'I' and 'SI', respectively.

A separate listing of all ECG parameters outside their reference range by subject will also be provided.

The reference ranges (from the Quotient SOP "The Interpretation of the Electrocardiogram, Vital Signs and Clinical Laboratory Data During Phase I / II Clinical Trials") and defined in Table 6 will be used.

Table 6 ECG Reference Ranges

Parameter	Split	Lower limit	Upper limit
Ventricular Rate (HR)	NA	40 bpm	100 bpm
QT Interval	NA	NA	500 msec
QTcF Interval	Male	NA	450 msec
PR Interval	NA	120 msec	220 msec
QRS Duration	NA	NA	120 msec
QRS Axis	NA	-30°	100°

HR=heart rate

NA=Not applicable

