14.3.2.4	Subjects Reporting Treatment-Emergent Adverse Events By MedDRA System Organ Class, Preferred Term and Relationship to IMP Summary Statistics: Safety Population Part 2: [14C]-KD025 Oral Capsule
14.3.2.5	Subjects Reporting Adverse Drug Reactions By MedDRA System Organ Class and Preferred Term Summary Statistics: Safety Population Part 2: [14C]-KD025 Oral Capsule
14.3.2.6	Subjects Reporting Serious Adverse Events By MedDRA System Organ Class and Preferred Term Summary Statistics: Safety Population Part 2: [14C]-KD025 Oral Capsule
	Laboratory Results
14.4.1.1	Haematology Summary Statistics: Safety Population Part 1: KD025 Oral Tablet & [14C]-KD025 IV Infusion
14.4.1.2	Haematology Shift Table: Safety Population Part 1: KD025 Oral Tablet & [14C]-KD025 IV Infusion
14.4.1.3	Clinical Chemistry Summary Statistics: Safety Population Part 1: KD025 Oral Tablet & [14C]-KD025 IV Infusion
14.4.1.4	Clinical Chemistry Shift Table: Safety Population Part 1: KD025 Oral Tablet & [14C]-KD025 IV Infusion

Table Number	Table Title
14.4.2.1	Haematology Summary Statistics: Safety Population Part 2: [14C]-KD025 Oral Capsule
14.4.2.2	Haematology Shift Table: Safety Population Part 2: [14C]-KD025 Oral Capsule
14.4.2.3	Clinical Chemistry Summary Statistics: Safety Population Part 2: [14C]-KD025 Oral Capsule
14.4.2.4	Clinical Chemistry Shift Table: Safety Population Part 2: [14C]-KD025 Oral Capsule
	Vital Signs and ECG Results
14.5.1.1	Vital Signs Summary Statistics: Safety Population Part 1: KD025 Oral Tablet & [14C]-KD025 IV Infusion
14.5.1.2.1	ECGs Summary Statistics: Safety Population Part 1: KD025 Oral Tablet & [14C]-KD025 IV Infusion
14.5.1.2.2	ECGs QTcF Categorical Data Summary Statistics: Safety Population Part 1: KD025 Oral Tablet & [14C]-KD025 IV Infusion
14.5.2.1	Vital Signs Summary Statistics: Safety Population Part 2: [14C]-KD025 Oral Capsule
14.5.2.2.1	ECGs Summary Statistics: Safety Population Part 2: [14C]-KD025 Oral Capsule
14.5.2.2.2	ECGs QTcF Categorical Data Summary Statistics: Safety Population Part 2: [14C]-KD025 Oral Capsule

18 Index of Figures

Figure Number	Figure Title
	Whole Blood and Plasma Pharmacokinetic Concentrations
14.2.2.1.1	Plasma Pharmacokinetic Concentrations Linear/Linear Scale Arithmetic Mean (\pm Arithmetic SD) Values: <PK Population/PK Analysis Dataset> Part 1: KD025 Oral Tablet & [14C]-KD025 IV Infusion < KD025 / [14C]-KD025 >

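### The 'Overall' QTcF row promises each subject's worst value, but unscheduled ECGs are kept out of the summaries, so as written it reports only the worst scheduled value

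*SAP*

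**What the plan says.** SAP 10.6.1 plans counts of subjects by QTcF category and by category of QTcF increase from baseline, at each time point within each study part, plus an 'Overall' count. For the latter: "For 'Overall' counts the worst (highest) value for each subject will be used for the counts". The sentence does not restrict the values to scheduled ECGs.

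SAP 10.6.2, on listings, says that unscheduled ECGs are listed with a '#' "to indicate it will not be used in the summary statistics". The index of tables (SAP Section 17) gives the title of the categorical tables, 14.5.1.2.2 and 14.5.2.2.2, as "QTcF Categorical Data Summary Statistics: Safety Population".

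The protocol provides for ECGs outside the schedule in two places. Section 14.7: "If a subject shows an abnormal assessment at any stage, repeat measurements may be made and the abnormality followed to resolution if required" and "Additional measurements may be taken as deemed necessary by the investigator". Section 14.10 allows extra non-invasive procedures "if it is believed that an important effect of the IMP(s) is occurring or may occur at a time when no measurements are scheduled".

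SAP 13.1 allows an unscheduled assessment to stand in for a missing baseline. It gives no comparable allowance for a post-dose maximum.

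**The concern.** A worst-value count exists to catch an excursion whenever it happens. Unscheduled ECGs are not a random sample of readings: they are taken because something already looked abnormal or because an effect was suspected. Leaving them out of the by-time-point means is sensible, since they belong to no nominal time. Leaving them out of the one row that is meant to show the extreme works against the purpose of that row.

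At stake is whether a reader of the QTcF table can take an empty >500 msec or >60 msec cell in the 'Overall' row to mean that no such value was recorded. As the SAP stands, it means only that no such value was recorded at a scheduled time.

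The two rules also sit in different subsections. A programmer working from 10.6.1 alone could include unscheduled ECGs, while one working from both would exclude them, so the same plan can produce two different tables.

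**Working it through.** The plan states no figure for this point, so the check is mainly a reading of the passages against each other.

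**Step 1: does the exclusion reach the 'Overall' row?**

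| Source | Content | Consequence |
|---|---|---|
| SAP 10.6.1 | 'Overall' uses each subject's highest value | Defines the row as a maximum |
| SAP 10.6.2 | '#' ECGs are not used in summary statistics | Removes unscheduled ECGs from any output of that kind |
| SAP Section 17 | The QTcF categorical tables carry 'Summary Statistics' in their titles | The removal applies to these tables |
| SAP 13.1 | Unscheduled values may replace a missing baseline; no other safety imputation | No exception for a post-dose maximum |
| SAP Section 20, mock Table 14.5.1.2.2 | Baseline and time-point rows only | No 'Overall' row or footnote to settle the matter |

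The exclusion reaches the row. The maximum is taken over scheduled ECGs only. The SAP has no separate rule for repeat ECGs. They are not on the flow charts, so I treat them as unscheduled.

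**Step 2: is the conflict specific to QTcF?** SAP 10.4.2 and 10.5.2 apply the same '#' rule to laboratory data and vital signs, but the SAP states no worst-value row for either. The conflict arises only for QTcF.

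**Step 3: when does it change a count?**

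- A scheduled ECG is abnormal and the repeat is no higher: no change, because the scheduled value counts.
- A scheduled ECG is abnormal and the repeat falls in a higher category: the subject is counted one or more categories too low.
- The excursion is seen only on an ECG between scheduled times: the subject is counted by his scheduled readings alone.

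**Step 4: is there room for the third case?** The Part 1 flow chart (Protocol Appendix 2, SAP Appendix 1) shows no ECG between pre-dose and 4 h after the oral dose. Protocol 8.1.1 gives the expected oral Tmax as 2 h. In Part 1, an ECG near the expected Tmax could therefore only be unscheduled. There are two caveats from the extracted charts. The second post-dose ECG in Part 1 falls at 6 h in the protocol copy and at 5.75 h in the SAP copy, so its time is uncertain, though the gap before 4 h is the same in both. The Part 2 chart appears to have an ECG near 2 h, so this observation is for Part 1.

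**Step 5: size.** Six subjects are planned (SAP 5.2). Assume that one subject's value above 500 msec, or increase above 60 msec, appears only on an unscheduled ECG.

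- As planned: 0/6 = 0.0%.
- With all post-dose ECGs counted: 1/6 = 16.7%.
- If only 4 subjects contributed to the row, the comparison would be 0/4 = 0.0% against 1/4 = 25.0%.

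The documents give no basis for the probability of this case, so it is an illustration and not an expected error.

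**The case against.** The strongest reply is that the '#' rule is explicit and uniform across laboratory, vital-sign and ECG data, so 'worst value' can be read coherently as worst scheduled value. Relabelling the row would remove the tension without changing any count. Counting unscheduled ECGs also gives subjects with repeats more single readings from which to draw a maximum. Both points stand. The first makes a label the minimum remedy. The second is a real cost of the fuller one.

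It is also fair to say that little is hidden. Unscheduled ECGs are listed, ECG measurements carry H/L flags, QTcF increases carry I/SI flags, and out-of-range values have their own listing (SAP 10.6.2). Clinically significant ECG abnormalities are reported as adverse events (Protocol 14.7), and events leading to withdrawal are summarised (SAP 10.3.1.1). With 6 subjects, a reader can inspect every value. This limits the harm, but a listing does not correct a summary cell.

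A reader might infer three stronger things that the documents do not support.

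- That the protocol directs extra ECGs. Sections 14.7 and 14.10 only permit them.
- That a subject withdrawn under Protocol 8.3 for a confirmed QTc above 500 msec, or an increase above 60 msec, would be tabulated at <=450 msec and <30 msec. That needs every qualifying reading to be unscheduled and every scheduled reading to be in the lowest category. A qualifying scheduled ECG that triggered the repeat would still count.
- That the QTcF table would contradict the disposition table. Table 14.1.1 shows counts and reasons for discontinuation, not QTcF values. A discrepancy is possible, not implied.

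**Conclusion.** The point holds as an inconsistency between SAP 10.6.1 and 10.6.2: the row defined by each subject's worst value would report the worst scheduled value. It can place a subject in too low a QTcF or QTcF-increase category when his highest reading is on an unscheduled or repeat ECG. One such subject moves a category by 16.7 percentage points with 6 subjects.

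This rests on two readings: that '#' applies to every output titled as summary statistics, and that repeats count as unscheduled. Whether any count is actually wrong depends on data not yet seen.

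The consequence is limited to descriptive safety reporting. The primary endpoints are bioavailability, mass balance recovery and sample collection, and none of them uses this row. It should be corrected because the remedy is cheap and the row otherwise does not mean what it says.

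**What to change.** Make four edits to the SAP.

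1. In 10.6.1, derive the 'Overall' counts, for both QTcF and QTcF increase, from all post-dose ECGs in that study part, scheduled and unscheduled, including repeats.
2. Keep the by-time-point rows on scheduled ECGs only.
3. In 10.6.2, limit the '#' to mean not used in by-time-point summaries.
4. Add a post-baseline 'Overall' row to the mock QTcF table, with a footnote saying which ECGs it covers. This also settles whether baseline is included, which 10.6.1 leaves open.

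If the sponsor prefers to keep the exclusion, the minimum is to label the row as worst scheduled post-dose value.

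The cost is a few lines of SAP text and a small programming change, with no new data and no change to any by-time-point summary. The downside is that subjects with repeat ECGs contribute more readings to their maximum. Compared with a row built from scheduled post-dose ECGs, the counts can only stay the same or become less favourable. The edit does not touch the ECG schedule.
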